2.1 Primary Objective

- To analyze the effects of yoga and/or gentle massage practices + standard treatment versus standard treatment alone on symptom management in patients undergoing Hematopoietic Stem Cell Transplantation, assessed by the Edmonton Symptom Assessment Scale (ESAS). Primary Outcomes
- To analyze changes in ESAS in the domains of fatigue, pain, nausea, anxiety, and well-being before and after each of the 8 sessions.

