2.2 Secondary Objectives

- To analyze changes in the Quality of Life Scale during HSCT;
- To analyze changes in the Religiosity Scale during HSCT;
- To analyze the subjective experience of the patient during HSCT;
- To analyze patient satisfaction during HSCT. Secondary Outcomes
 - Changes in the Quality of Life Scale at 2 time points: upon admission and on Day 21 or at discharge (whichever occurs first);
 - Changes in the Religiosity Scale at 2 time points: upon admission and on Day 21 or at discharge (whichever occurs first);

- Open-ended question about the subjective experiences of patients undergoing HSCT on Day 21 or at discharge (whichever occurs first);
- Questions about patient satisfaction during HSCT on Day 21 or at discharge (whichever occurs first).

2.3 Hypothesis The practice of yoga and gentle massage combined with standard treatment is superior to standard treatment alone in symptom management in patients undergoing HSCT.

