postgraduate degrees in Yoga (Institute of Teaching and Research in Yoga - IEPY) and in Integrative Health Bases and Well-being (Albert Einstein Institute of Teaching and Research - IIEP). Group B (intervention) will receive a total of 8 individual integrative practice sessions at the bedside, each lasting 15 to 20 minutes, with 2 sessions per week during the following periods: • from admission until Day 0 • until Day 7 • until Day 14 • until Day 21 or discharge. The therapist will choose the integrative practices that best suit the patient for each session, according to their psychophysical state and presented symptoms, as there are many variations during HSCT. Group A (control) will receive 8 visits from integrative therapists who will remain in the patient's room, able to interact but without offering integrative practices, during the same period described above. After Day 21, these patients will also receive 8 integrative practice sessions at the bedside or in the Integrative Medicine room. If any patient from this group needs to receive Integrative Medicine care, they will receive it and be withdrawn from the study.

3.5.1 Yoga Yoga sessions will be conducted at the patient's bedside, in a supine or sitting position, using one or more of the following techniques: gentle stretches (asanas), guided relaxation (savasana), deep and slow diaphragmatic breathing (pranayama), and meditative exercises focusing on natural breathing or visualizing a place that brings well-being (dhyana). Based on these techniques, the integrative therapist will choose what best suits the patient for each session, according to their psychophysical state and presented symptoms, as there are many variations during HSCT. Non-violence (ahimsa) as a basic and essential principle of yoga practice will be reiterated in each class to encourage participants to be gentle with themselves and accept possible limitations.

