3.5.2 Massage Gentle massage involves gentle touches, using light pressure, mainly with the palm, with a slow and steady rhythm over the entire body. It can be performed over clothing and even over the sheet and blanket. The sequence of light touches begins at the head, moving down the right shoulder, arm, forearm, and right hand; thigh, knee, leg down to the right foot, where it will be gently massaged on the back, fingers, and sole of the right foot. Afterward, the therapist's hands move up in the reverse sequence on the left side of the patient's body, finishing again at the head. The action of this technique is on the skin and not on the muscles. Sensory information from this gentle touch on the epidermis activates the Relaxation Response in the Autonomic Nervous System, increasing the stimulation of the PNS and decreasing the excitement of the SNS.

3.6 Assessments The scales and questionnaires will be digitally administered through the REDCap Einstein platform. Only the Qualitative Report will be provided in printed form for the patient to describe their experience. All these documents are available in the appendices of this project.

3.6.1 Edmonton Symptom Assessment Scale - ESAS-Br The Edmonton Symptom Assessment Scale - ESAS-Br will be used before and after each of the 8 sessions in both groups, assessing the domains: pain, fatigue, nausea, anxiety, and well-being.

3.6.2 Functional Assessment Cancer Therapy - Bone Marrow Transplantation Quality of Life Scale - FACIT-BMT The Functional Assessment Cancer Therapy - Bone Marrow Transplantation Quality of Life Scale - FACIT-BMT will be used at two time points: upon admission and on Day 21 (or at discharge).

3.6.3 Duke Religious Index - DUREL The Duke Religious Index - DUREL will be applied at two time points: upon admission and on Day 21 (or at discharge).

3.6.4 Qualitative Report The Qualitative Report will be handed to the patient in printed form on Day 21 (or at discharge), using an open-ended question for the patient to describe: "What was your experience with Integrative Medicine like?"

3.6.5 Patient-Reported Experience Measures (PREMs) To assess patient satisfaction and experience, the Patient-Reported Experience Measures (PREMs) will be applied on Day 21 (or at discharge).

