3.7 Statistical Analysis The qualitative characteristics of patients will be described according to groups using absolute and relative frequencies, and associations with the groups will be verified using chi-square tests or exact tests, while quantitative characteristics will be described according to groups using summary measures (mean, standard deviation, median, minimum, and maximum), and group comparisons will be made using t-Student tests or Mann-Whitney tests depending on the probability distribution of the data. Mean changes in each ESAS domain over the 8 therapy sessions will be calculated, and group means on the scales will be compared using t-Student tests or Mann-Whitney tests. The analyses will be performed using IBM-SPSS software for Windows version 22.0, tabulated using Microsoft-Excel 2010 software, and tests will be conducted at a 5% significance level.

4. ETHICAL ASPECTS This project will be submitted for review to the Research Project Management System of the Albert Einstein Israelite Hospital (HIAE), the institution hosting the Einstein Family Dayan - Daycoval Oncology and Hematology Center. Subsequently, it will be submitted to the Brazil Platform and the institutional Research Ethics Committee. All patients will sign the Informed Consent Form because it involves human subjects.

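### The primary outcome measures relief across each 15 to 20 minute session and gives no credit for benefit that lasts between sessions, although the objective and hypothesis concern symptom management during transplantation

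*Protocol*

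**What the plan says.** Section 2.1 asks about symptom management under the practices plus standard treatment against standard treatment alone, assessed with ESAS. The hypothesis in section 2.3 is that the combination "is superior to standard treatment alone in symptom management". The primary outcome in section 2.1 is "To analyze changes in ESAS in the domains of fatigue, pain, nausea, anxiety, and well-being before and after each of the 8 sessions".

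Under section 3.6.1, ESAS "will be used before and after each of the 8 sessions in both groups, assessing the domains: pain, fatigue, nausea, anxiety, and well-being". No other ESAS time point is scheduled. Section 3.5 describes eight sessions, "each lasting 15 to 20 minutes, with 2 sessions per week during the following periods", the last period running "until Day 21 or discharge". Control patients receive eight therapist visits over the same period.

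For the analysis, section 3.7 states: "Mean changes in each ESAS domain over the 8 therapy sessions will be calculated, and group means on the scales will be compared", by t or Mann-Whitney test. The sample size in section 3.3 starts from a one-session pilot improvement in fatigue. The secondary outcomes in section 2.2 include quality of life at admission and at Day 21 or discharge, but no comparison of ESAS levels between arms.

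**The concern.** The question is about symptoms over an admission of several weeks. The outcome looks only at the minutes around each session. A before-to-after change is a clean measure at session 1, where the before score precedes any study treatment. From session 2 the before score is itself a post-randomisation measurement. If yoga or massage leaves a patient better off several days later, that gain sits in the next before score and is subtracted out.

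The arms could therefore differ in symptom level throughout the admission without that difference entering the primary result. Conversely, a positive result could reflect relief that fades soon after the therapist leaves, and still be reported as superior symptom management. The pre-session scores at sessions 2 to 8 would tell these cases apart. They are collected in both arms, but no outcome or analysis stated in the protocol compares them.

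**Working it through.** **The plan's own figure.** Inputs from section 3.3: difference 1.5 points, SD 1.58, 80% power, 95% confidence (taken as two-sided 5%). The normal formula gives n = 2 × (1.960 + 0.842)² × (1.58/1.5)² = 17.4, so 18 per group, as stated. A t-based solution gives 18.4, so 19. With the planned 20 per group, t-test power is 83%. The sample-size arithmetic is not at fault.

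**What the outcome counts.** Let b be the advantage of the intervention arm just after a session and p the share of it still present at the next pre-session rating. The documents give no value for p, so it is an assumption and is shown over its range. Control is taken as unchanged across visits.

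*Model 1, capped benefit.* Every session brings the patient to 1.5 points below control. The within-session difference is 1.5 at session 1 and 1.5 × (1 − p) at sessions 2 to 8, so the mean is 1.5 × [1 + 7(1 − p)]/8. The pre-session difference at sessions 2 to 8 is 1.5 × p. Power is for 20 per arm with SD 1.58.

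| p | Mean within-session difference | Pre-session difference, sessions 2 to 8 | Power |
|---|---|---|---|
| 0 | 1.50 | 0 | 83% |
| 0.5 | 0.84 | 0.75 | 38% |
| 1 | 0.19 | 1.50 | 6.5% |

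*Model 2, proportional benefit.* Each session removes 25% of the current score, from an assumed level of 6. As p goes from 0 to 1, the mean within-session difference falls from 1.50 to 0.68 and power from 83% to 26%. The pre-session benefit, averaged over all eight sessions, rises from 0 to 3.3 points.

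*Model 3, additive benefit.* Each session lowers the current score by 1.5, whatever that score is. The within-session difference stays at 1.5 for every p until the scale floor is reached, so it does not shrink. At p = 0.5 the pre-session differences at sessions 2 to 8 run 0.75, 1.13, 1.31, 1.41, 1.45, 1.48 and 1.49, mean 1.29. None of this enters the outcome.

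**The SD behind the power figures.** The 1.58 comes from one pilot session, but the analysed quantity is a mean over eight. If session changes share a correlation r, the SD of the mean is 1.58 × √[(1 + 7r)/8]. It equals 1.58 only at r = 1. Power at 0.84 points with 20 per arm:

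| r (assumed) | SD of the mean | Power |
|---|---|---|
| 1.0 | 1.58 | 38% |
| 0.7 | 1.36 | 48% |
| 0.5 | 1.19 | 59% |
| 0.2 | 0.87 | 85% |

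At 0.19 points, power stays between 6.5% and 10% over the same range of r.

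**The case against.** The strongest reply is that immediate relief is a legitimate form of symptom management. The outcome, the one-session pilot and the analysis agree with one another on it, and the protocol never promises durable control. That stands as a defence of keeping the outcome. It does not justify an unqualified claim about symptom management from it.

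A reader might infer that the outcome always penalises lasting benefit, scoring best when relief vanishes and worst when it persists. The documents do not support that: it follows under capped or proportional benefit, but not under additive benefit. A reader might also take 38% as the trial's power. That figure needs half carry-over, a cap and perfectly correlated session changes, none of which the documents state. Full carry-over across several days is an extreme case.

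Section 3.7 is also open to another reading, since a mean change over the eight sessions could mean change over the course. Section 2.1 and the single-session pilot in section 3.3 favour the within-session reading, but the wording should be settled either way. A statistical analysis plan, not shown, might model the repeated scores. The primary outcome and its summary measure are nevertheless fixed in this protocol.

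Finally, the control visits balance therapist contact, though not the expectation of receiving a practice, and quality of life does cover the admission. It is, however, a secondary outcome and not ESAS.

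**Conclusion.** The concern holds in a limited form. As defined, the primary outcome measures immediate relief around each session and gives no credit for benefit that lasts to the next one. That is true in all three models and needs no assumed figure. Whether the measured difference also shrinks, and by how much, depends on how benefit accumulates and on carry-over, both unknown. The range runs from no shrinkage (additive benefit, or no carry-over) to 0.19 of 1.50 points (full carry-over under a cap). The corresponding power also depends on how session changes correlate.

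It would be too strong to say that the trial cannot answer its question. The pre-session scores needed are collected in both arms, so the limitation lies in the stated outcome and analysis, not in the data. This is a worthwhile and cheap improvement, not a fatal flaw.

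**What to change.** - In sections 2.1 and 3.7, say explicitly that the outcome is the change from before to after each session, averaged over sessions, and that it measures immediate relief. Limit the claim from it to that.
- Prespecify a between-arm analysis of the pre-session ESAS scores at sessions 2 to 8: a mixed model with group, session and the session-1 pre-session score as covariate. Rest any claim about symptom management over the admission on this analysis.

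No new visits or data are needed. The cost is one more analysis, which needs a place in the testing order. These scores are also unblinded self-reports, so the change does not remove the open-label limitation.

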2.2 Secondary Objectives

- To analyze changes in the Quality of Life Scale during HSCT;
- To analyze changes in the Religiosity Scale during HSCT;
- To analyze the subjective experience of the patient during HSCT;
- To analyze patient satisfaction during HSCT. Secondary Outcomes
 - Changes in the Quality of Life Scale at 2 time points: upon admission and on Day 21 or at discharge (whichever occurs first);
 - Changes in the Religiosity Scale at 2 time points: upon admission and on Day 21 or at discharge (whichever occurs first);

- Open-ended question about the subjective experiences of patients undergoing HSCT on Day 21 or at discharge (whichever occurs first);
- Questions about patient satisfaction during HSCT on Day 21 or at discharge (whichever occurs first).

2.3 Hypothesis The practice of yoga and gentle massage combined with standard treatment is superior to standard treatment alone in symptom management in patients undergoing HSCT.

3. METHOD

3.1 Population The study will be conducted at the Albert Einstein Israelite Hospital - Morumbi Unit, with patients admitted to the Oncology and Hematology Center for Bone Marrow Transplantation. Only after obtaining Informed Consent (ICF) acceptance, the patient's clinical and sociodemographic variables during hospitalization will be extracted from the electronic medical record of the institutional database: age, gender, month/year and type of transplant, conditioning intensity, donor type, cell source, and underlying disease.

3.1.1 Inclusion Criteria

- Adults aged 18 and older;
- Admitted to the HIAE, eligible for Bone Marrow Transplantation;
- Patients who speak and read Portuguese.

3.1.2 Exclusion Criteria

- Patients with hearing impairment;
- Patients previously diagnosed with psychiatric disorders: schizophrenia.

3.2 Experimental Design This is a prospective open-label randomized study evaluating the practice of yoga and gentle massage combined with standard treatment versus the use of standard treatment alone.

3.3 Sample Size The sample will consist of a total of 40 patients for this study. Based on a pilot sample (N = 40) with only one session of yoga + gentle massage, an improvement of 1.58 points (SD = 1.58 points) in fatigue was observed. Aiming to find an average difference of at least 1.5 points between the intervention group (yoga + gentle massage + standard treatment) and the control group (exclusive standard treatment) over 8 proposed sessions, with 80% power and 95% confidence, a sample of 18 patients in each group would be required. Since, in addition to fatigue, other parameters such as pain, nausea, anxiety, and well-being will be evaluated, we will use a sample of at least 20 patients per group to also account for these parameters, totaling at least 40 patients in the study.

3.4 Randomization Randomization will be performed according to the randomization block generated by Excel and will be carried out using the REDCap tool. Thus, upon accepting participation in the protocol, each patient will receive an individual number that will be included in this randomization block, with the sequence of their participation in the protocol predetermined by the Excel table to be inserted into REDCap and randomized according to parameterization, stratified by age groups: 18 to 30 / 31 to 50 / 51 to 65 / over 66 years 18 to 40 / 41 to 60 / above 61 years and by type of transplant: autologous, allogeneic, and umbilical cord.

3.5 Training Program During the HSCT period, patients will be randomized into two groups:

- Group A (control): standard treatment
- Group B (intervention): yoga or gentle massage plus standard treatment

The intervention sessions will be verbally conducted by integrative therapists from the Integrative Medicine Team, hired by the Oncology and Hematology Center of HIAE, all with

postgraduate degrees in Yoga (Institute of Teaching and Research in Yoga - IEPY) and in Integrative Health Bases and Well-being (Albert Einstein Institute of Teaching and Research - IIEP). Group B (intervention) will receive a total of 8 individual integrative practice sessions at the bedside, each lasting 15 to 20 minutes, with 2 sessions per week during the following periods: • from admission until Day 0 • until Day 7 • until Day 14 • until Day 21 or discharge. The therapist will choose the integrative practices that best suit the patient for each session, according to their psychophysical state and presented symptoms, as there are many variations during HSCT. Group A (control) will receive 8 visits from integrative therapists who will remain in the patient's room, able to interact but without offering integrative practices, during the same period described above. After Day 21, these patients will also receive 8 integrative practice sessions at the bedside or in the Integrative Medicine room. If any patient from this group needs to receive Integrative Medicine care, they will receive it and be withdrawn from the study.

3.5.1 Yoga Yoga sessions will be conducted at the patient's bedside, in a supine or sitting position, using one or more of the following techniques: gentle stretches (asanas), guided relaxation (savasana), deep and slow diaphragmatic breathing (pranayama), and meditative exercises focusing on natural breathing or visualizing a place that brings well-being (dhyana). Based on these techniques, the integrative therapist will choose what best suits the patient for each session, according to their psychophysical state and presented symptoms, as there are many variations during HSCT. Non-violence (ahimsa) as a basic and essential principle of yoga practice will be reiterated in each class to encourage participants to be gentle with themselves and accept possible limitations.

3.5.2 Massage Gentle massage involves gentle touches, using light pressure, mainly with the palm, with a slow and steady rhythm over the entire body. It can be performed over clothing and even over the sheet and blanket. The sequence of light touches begins at the head, moving down the right shoulder, arm, forearm, and right hand; thigh, knee, leg down to the right foot, where it will be gently massaged on the back, fingers, and sole of the right foot. Afterward, the therapist's hands move up in the reverse sequence on the left side of the patient's body, finishing again at the head. The action of this technique is on the skin and not on the muscles. Sensory information from this gentle touch on the epidermis activates the Relaxation Response in the Autonomic Nervous System, increasing the stimulation of the PNS and decreasing the excitement of the SNS.

3.6 Assessments The scales and questionnaires will be digitally administered through the REDCap Einstein platform. Only the Qualitative Report will be provided in printed form for the patient to describe their experience. All these documents are available in the appendices of this project.

3.6.1 Edmonton Symptom Assessment Scale - ESAS-Br The Edmonton Symptom Assessment Scale - ESAS-Br will be used before and after each of the 8 sessions in both groups, assessing the domains: pain, fatigue, nausea, anxiety, and well-being.

3.6.2 Functional Assessment Cancer Therapy - Bone Marrow Transplantation Quality of Life Scale - FACIT-BMT The Functional Assessment Cancer Therapy - Bone Marrow Transplantation Quality of Life Scale - FACIT-BMT will be used at two time points: upon admission and on Day 21 (or at discharge).

3.6.3 Duke Religious Index - DUREL The Duke Religious Index - DUREL will be applied at two time points: upon admission and on Day 21 (or at discharge).

3.6.4 Qualitative Report The Qualitative Report will be handed to the patient in printed form on Day 21 (or at discharge), using an open-ended question for the patient to describe: "What was your experience with Integrative Medicine like?"

3.6.5 Patient-Reported Experience Measures (PREMs) To assess patient satisfaction and experience, the Patient-Reported Experience Measures (PREMs) will be applied on Day 21 (or at discharge).

3.7 Statistical Analysis The qualitative characteristics of patients will be described according to groups using absolute and relative frequencies, and associations with the groups will be verified using chi-square tests or exact tests, while quantitative characteristics will be described according to groups using summary measures (mean, standard deviation, median, minimum, and maximum), and group comparisons will be made using t-Student tests or Mann-Whitney tests depending on the probability distribution of the data. Mean changes in each ESAS domain over the 8 therapy sessions will be calculated, and group means on the scales will be compared using t-Student tests or Mann-Whitney tests. The analyses will be performed using IBM-SPSS software for Windows version 22.0, tabulated using Microsoft-Excel 2010 software, and tests will be conducted at a 5% significance level.

4. ETHICAL ASPECTS This project will be submitted for review to the Research Project Management System of the Albert Einstein Israelite Hospital (HIAE), the institution hosting the Einstein Family Dayan - Daycoval Oncology and Hematology Center. Subsequently, it will be submitted to the Brazil Platform and the institutional Research Ethics Committee. All patients will sign the Informed Consent Form because it involves human subjects.

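### The hypothesis and sample size name standard treatment alone as comparator, but controls also get 8 therapist visits; and 3.3 gives no inputs for the four further primary domains it says 20 per group accounts for

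*Protocol*

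**What the plan says.** **Comparator.** Five places in the protocol name it without the visits:

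- 2.1, primary objective: "standard treatment versus standard treatment alone on symptom management".
- 2.3, hypothesis: the practices "combined with standard treatment is superior to standard treatment alone in symptom management".
- 3.2, design: "versus the use of standard treatment alone".
- 3.3, sample size: "the control group (exclusive standard treatment) over 8 proposed sessions".
- 3.5, list of groups: "Group A (control): standard treatment".

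Later in 3.5, each control patient is scheduled for 8 visits by the integrative therapists over the same period as the intervention sessions. Interaction is allowed; the practices are not offered. Section 3.6.1 applies ESAS before and after each of the 8 sessions in both arms.

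**Sample size.** Section 3.3 uses a pilot of 40 patients with a single session, in which fatigue improved by 1.58 points (SD 1.58). The target is stated as "Aiming to find an average difference of at least 1.5 points between the intervention group" and control, with 80% power and 95% confidence, which gives 18 per group. For pain, nausea, anxiety and well-being it adds: "we will use a sample of at least 20 patients per group to also account for these parameters". Section 2.1 places these four beside fatigue under the primary outcomes: "To analyze changes in ESAS in the domains of fatigue, pain, nausea, anxiety, and well-being before and after each of the 8 sessions".

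**The concern.** A control arm with scheduled, interactive visits from the same therapists is not the arm that the hypothesis describes. The outcomes are self-reported and the trial is open-label, so contact alone could plausibly move domains such as anxiety and well-being. The visits are a reasonable way to control for attention. The difficulty is that a result against this arm would be reported as a result against standard treatment alone. The sample size inherits the same label, and its 1.5-point target comes from a pilot for which no control group is reported.

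The closing sentence of 3.3 invites a second misreading. If a reader takes 20 per group as adequate for all five primary domains, a null result for pain or nausea may be read as absence of effect, although no calculation for those domains is shown.

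**Working it through.** **1. Comparator.** No arithmetic is needed; the sections can be set side by side.

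- Named in 2.1, 2.3, 3.2, 3.3 and the Group A line of 3.5: standard treatment, called alone or exclusive in the first four.
- Described later in 3.5: standard treatment plus 8 therapist visits with interaction allowed.
- Measured under 3.6.1: ESAS change around each session in both groups, so the control change is taken around the visits.

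The difference between arms is then (practices + therapist contact + standard treatment) minus (therapist contact + standard treatment). That is the contribution of the practices over and above the visits.

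**2. The plan's own figure.** Inputs from 3.3: difference 1.5, SD 1.58, power 80%, confidence 95%. Sidedness is not stated; two-sided 5% is assumed, and it reproduces the stated 18 (one-sided would give 14).

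n = 2 × (1.960 + 0.842)² × (1.58/1.5)² = 17.42, so 18 per group. The figure reproduces.

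**3. What 20 instead of 18 achieves.** Section 3.7 names the t test (or Mann-Whitney). For the t test, d = 1.5/1.58 = 0.949, noncentrality = d × √(n/2), df = 2n − 2.

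- n = 18: noncentrality 2.85, power 79.0%.
- n = 20: noncentrality 3.00, power 83.3%.
- Standardised difference detectable with 80% power: 0.961 at 18 and 0.909 at 20. At SD 1.58 this is 0.961 × 1.58 = 1.52 points and 0.909 × 1.58 = 1.44 points.

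**4. The other four domains.** The protocol gives no difference and no SD, so power cannot be computed. For illustration only, take a 1.5-point difference and assumed SDs of 2.0, 2.5 and 3.0. The t-test power at 20 per group is then about 64%, 46% and 34%. With the fatigue inputs it would be 83.3%. The range shows only that the answer depends on figures that are not given.

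**5. Where the comparator meets the sample size.** The target of 1.5 is close to the pilot improvement of 1.58. If the intervention arm repeated the pilot, a 1.5-point difference would leave 1.58 − 1.5 = 0.08 points for improvement in controls. If the visits reduced the difference by 0.25, 0.5 or 0.75 points (assumed), it would become 1.25, 1.0 or 0.75. With SD 1.58 and 20 per group, power would be about 68%, 50% or 31%.

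**6. The SD works in the other direction.** The 1.58 is the SD of a one-session change, while 3.7 analyses the mean change over 8 sessions. With equal session SDs and between-session correlation ρ, the SD of the mean is 1.58 × √((1 + 7ρ)/8), which cannot exceed 1.58. At an assumed ρ = 0.5 it is 1.58 × 0.75 = 1.19, and power for 1.5 points at 20 per group is about 97%. The 83.3% is therefore conditional on both the SD and the target.

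**The case against.** **On the comparator.** Section 3.5 describes in full what controls receive, so no site would deliver the wrong arm. Standard treatment can be read as the therapy, with the visits as an attention control that strengthens an open-label design, and ESAS in both arms is balanced measurement. All of this stands as a defence of the design. It does not reconcile the hypothesis with the arm: alone and exclusive do not describe eight scheduled interactive visits.

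A reader might go further and infer that the trial will understate the effect against standard treatment alone. The protocol does not support that, because nothing in it reports that the visits ease symptoms. Understatement follows only if they do.

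**On the sample size.** Section 3.3 is open that its calculation is for fatigue, and it never states 80% power for the other domains. Sizing on one domain and rounding up is common. This stands, and it is why the point is secondary. Two stronger readings are tempting and neither holds:

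- That 18 is wrong. It is correct by the normal formula; the t-test version needs 18.4, hence 19, and the planned 20 exceeds both.
- That the trial is shown to be underpowered for pain, nausea, anxiety or well-being. Without inputs this cannot be shown in either direction.

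A separate statistical analysis plan could add detail, but both statements at issue are made in the protocol itself.

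**Conclusion.** The comparator point holds as written in the protocol: the objective, hypothesis, design statement, sample size and Group A line name a contrast that the control procedure in 3.5 does not deliver. The trial can conclude on what the practices add to standard treatment plus therapist visits. It does not isolate the contrast with standard treatment alone. The size of any gap between the two is unknown, because no effect of the visits is reported.

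The sample-size point also holds, with less weight. The move from 18 to 20 per group adds 4.3 percentage points of power for fatigue (83.3 − 79.0) and lowers the detectable difference by 0.08 points (1.52 − 1.44). It does not document coverage of four more primary domains. The claim is unsupported, not shown to be false.

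These figures assume a two-sided 5% t test, 20 patients analysed per group and SD 1.58 for the mean change. The power values for other SDs, for control improvement and for between-session correlation are illustrations on assumed inputs.

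**What to change.** **Comparator.** Reconcile 2.1, 2.3, 3.2, 3.3 and the Group A line of 3.5 with the control procedure in 3.5, so that the comparator reads throughout: *standard treatment plus 8 therapist visits without integrative practices*. Limit the hypothesis, and any conclusion drawn from the trial, to that contrast.

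**Sample size.** Keep at least 20 per group and at least 40 in total. In the last sentence of 3.3, replace the clause about the other parameters with:

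> The sample size rests on fatigue: with 20 analysed per group, power is about 83% (two-sided 5%, t test) for a 1.5-point difference if the SD of the mean change over 8 sessions is 1.58, the SD of the single-session change in the pilot. The 1.5-point target is close to the pilot improvement of 1.58 points, for which no control group is reported, so power is lower if controls also improve with the visits. No power is stated for pain, nausea, anxiety and well-being.

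If the pilot recorded the other four domains, give each one's difference and SD in place of the last sentence. Do not write in a figure for patients lost from analysis: 3.5 withdraws controls who need Integrative Medicine care, but the protocol gives no rate.

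**Cost.** Rewording only, with no added patients and no change to either arm. The hypothesis becomes narrower, and the protocol gives up the suggestion that the sample was sized for all five domains.
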